## 6.7 Safety Measures

### Risks

The risk of adverse medical or psychiatric events should be minimized by the careful screening procedures to be used. The principal risks during the group lifestyle modification program include:

**Risk of gallstones.** Rapid weight loss may increase the risk of gallstones. The risk of gallbladder disease will be reduced by limiting weight loss to no more than 3 pounds per week for 3 consecutive weeks. Weight loss will be monitored at all group sessions. Patients will be asked to slow or stop their weight loss if there are concerns about the rate of their weight loss.

**Psychological distress.** Participants may become distressed by learning about and discussing their experiences with weight-based discrimination and stigma.

**Confidentiality and loss of privacy.** All efforts will be made to protect participant confidentiality and privacy. We cannot guarantee total privacy. Personal information may be given out if required by law.

### Ongoing medical visits and safety measures

A physician/nurse practitioner will be available if participants notice any side effects of weight loss. Participants who report significant depression or emotional distress will be

evaluated by the study's psychologist or psychiatrist and referred to their PCP for further evaluation and treatment. Participants will be referred to their PCP if their mood is significantly disrupting their normal function (as reflected by symptoms that include feeling blue, not enjoying usual activities, trouble sleeping or concentrating, or having thoughts of dying or harming oneself).

## 7. STATISTICAL ANALYSIS

### 7.1 Sample Size Calculation

A power analysis was conducted for the **primary outcome: reduction in Weight Bias Internalization Scale (WBIS) scores at week 12**. Estimated group means, attrition rate, intraclass correlation (ICC), and variances were derived from data from prior studies conducted at our Center. Specifically, we predict a 12-week reduction of 1.5 points on the WBIS in the BWL + BIAS group and 1 point in the BWL group, with expected standard deviations of 1. Based on these estimates, a baseline sample size of 72 participants (36 per group), assuming a 20% attrition rate, will give us 95% power to detect a between-treatment group difference at week 12 of 1 point to be significant at alpha = 0.05. The power analysis was conducted using G\*Power 2. All secondary outcomes will be considered exploratory and will provide valuable findings that will help to inform larger studies. This study has not been powered to detect differences in changes in other psychosocial and behavioral outcomes, weight loss, and cardiometabolic outcomes.

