## 2.4 Addressing weight stigma in weight loss interventions.

Weight stigma is not addressed as part of standard behavioral weight loss treatment. The few studies that have investigated the effects of weight loss on WBI have found an approximate  $\frac{1}{2}$  point reduction on the 7-point Weight Bias Internalization Scale following BWL, suggesting minimal improvement. This is consistent with prior research showing that the benefits of weight loss tend to be greater for physical health than for mental health and other aspects of psychosocial functioning. In contrast to BWL, recent preliminary evidence suggests that targeted psychological interventions may reduce WBI in patients with obesity. A pilot study of the Weight Bias Internalization and Stigma (BIAS) program showed that, in 8 patients with obesity and high levels of WBI, an 8-week cognitive-behavioral intervention reduced scores on the WBIS by approximately 1 point. This change was significantly greater than that found in a quasi-control group of 6 patients (partial eta = .36). The BIAS program also led to significantly greater reductions in negative stereotype endorsement (partial eta = .39) and increases in weight self-efficacy (partial eta = .47) than the quasi-control group.

Additionally, weight losses achieved with BWL treatment are not maintained, on average, in the long-term. Weight regain may be associated with deterioration in HRQOL and increases in WBI. An intervention that combines traditional BWL with a program to reduce WBI could produce clinically meaningful short- and long-term reductions in self-stigmatization, along with other psychological benefits, that persist independent of weight loss and regain. Additionally, given, the evidence reviewed that individuals who have experienced and/or internalized weight stigma have reduced self-efficacy for and engagement in weight management behaviors (e.g., physical activity), an intervention targeting weight stigma may improve long-term weight loss. Overall, an intervention that incorporates elements from both BWL and stigma-reduction approaches could provide patients with multifaceted health benefits.

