### 7.2 Analysis Plan

Data quality and integrity will be checked by assessing the data for missing and out-of-range values with basic statistical procedures, including univariate statistics and visual graphical displays (e.g., scatter plots). We will investigate all questions of data quality and integrity prior to performing any statistical modeling. To test the adequacy of randomization, preliminary analyses will include a comparison of all participant demographic and baseline characteristics by randomized treatment groups (t-tests or Wilcoxon rank sum tests for continuous variables and Chi-Square test or Fisher's Exact test for categorical data). If imbalances are observed, the relevant variables will be included as covariates in the final analyses.

All data will be analyzed under the intention-to-treat principle. Analyses will be two-tailed with a significance level of 0.05, and will be conducted using SPSS version 24.0 or SAS version 9.4. Participants who were randomized but did not attend a group meeting will not be included in the analyses, as they will not have received a dose of treatment. We will include as baseline covariates any variables that differ significantly between the treatment groups at baseline and show significant relationships with the outcome. To assess changes in WBIS scores across the 26-week trial, a mixed effects model will be fit with Treatment Group (*BWL+BIAS, BWL*) as a between subjects factor and Time (*Weeks 12 and 26*) as a categorical within-subjects factor. We will use the group x time interactions with the time main effect to estimate and test treatment group differences at each time point. In fitting a mixed effects model with residual maximum likelihood (REML), a variance-covariance structure must be selected. The criteria for selecting the best form of the variance-covariance structure will be based on criteria such as the Akaike's Information Criterion (AIC). The results from the mixed model will be summarized by mean (SE) for each treatment group at each time point. Residual analyses will be conducted to check for outliers and

influential points and violations in the normality assumption. If violations are detected, variance-stabilizing transformations will be considered.

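### Section 7.1 predicts a 0.5-point difference in WBIS reduction but claims 95% power for a 1-point difference; for 0.5 point the power is about 46%

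*Combined protocol and SAP*

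**What the plan says.** Section 7.1 (Sample Size Calculation) names the primary outcome as "reduction in Weight Bias Internalization Scale (WBIS) scores at week 12". It gives the planning values: "we predict a 12-week reduction of 1.5 points on the WBIS in the BWL + BIAS group and 1 point in the BWL group". The assumed SD is 1 in both arms. The sample size is 72 randomised, 36 per group, with 20% attrition. The next sentence, introduced as resting on those values, claims "95% power to detect a between-treatment group difference at week 12 of 1 point to be significant at alpha = 0.05".

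Section 7.2 (Analysis Plan) fixes the sidedness: "Analyses will be two-tailed with a significance level of 0.05".

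Section 2.4, in the background, puts the change after standard treatment at about one half "point reduction on the 7-point Weight Bias Internalization Scale following BWL", citing references 37 and 38. Section 7.1 cites the same two references, with reference 41, for its predicted reductions. Section 2.4 also reports a reduction of about 1 point in the BIAS pilot (reference 41).

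**The concern.** Two consecutive sentences give two different effects. The predicted reductions differ by 1.5 − 1.0 = 0.5 point, whereas the power is stated for 1 point. The second sentence claims to follow from the first, and it does not. No clinically important difference is offered as a separate reason for choosing 1 point.

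Section 7.1 says that the study is not powered for the other psychosocial and behavioural outcomes, weight loss or cardiometabolic outcomes. The confirmatory claim (hypothesis H1a) therefore rests on this one statement. If 1 point is the intended prediction for BWL, the trial is slightly more likely than not to miss the effect that it expects. A non-significant week-12 result would then be read as coming from a trial with 95% power, when for the predicted effect the power was less than half that. If instead the BWL figure is a misprint, the power claim stands, but the published planning assumption is wrong and disagrees with Section 2.4.

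**Working it through.** **Inputs**
- SD 1 in each arm, attached to the predicted reductions (Section 7.1).
- Alpha 0.05 (Section 7.1), two-sided (Section 7.2).
- 36 randomised per arm and 20% attrition (Section 7.1), so n = 36 × 0.8 = 28.8 evaluable per arm. Whole numbers 28 and 29 are shown as a check.
- Difference δ: 1.0 point (power sentence) or 1.5 − 1.0 = 0.5 point (predicted reductions).

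**Formula.** Two-sample t-test with df = 2n − 2 and noncentrality λ = δ / (SD × √(2/n)). Power is the probability that a noncentral t variable with these parameters exceeds the two-sided critical value in absolute size. At n = 28.8, df = 55.6, the critical value is 2.004 and √(2/28.8) = 0.2635.

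**Step 1: reproduce the stated figure.** With δ = 1.0, λ = 1.0 / 0.2635 = 3.795 and power is 96.2%. The stated 95% is therefore right for a 1-point difference, two-sided, after attrition.

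**Step 2: the difference that the plan predicts.** With δ = 0.5, λ = 0.5 / 0.2635 = 1.897 and power is 46.2%.

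| Evaluable per arm | Power, 1.0 point | Power, 0.5 point |
|---|---|---|
| 28 | 95.7% | 45.1% |
| 28.8 | 96.2% | 46.2% |
| 29 | 96.3% | 46.5% |
| 36 (no attrition) | 98.7% | 55.3% |

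**Step 3: could another convention rescue 95% for 0.5 point?** A one-sided test at 28.8 per arm gives 59.1%. The normal approximation, two-sided, gives 47.5%. Neither comes close, and nor does the no-attrition row above.

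**Step 4: what the sample can detect.** With 28.8 per arm, power is 80% at about 0.75 point and 95% at about 0.97 point.

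**Step 5: size needed for 0.5 point** (for scale only)
- 80% power: 64 evaluable per arm; 64 / 0.8 = 80 per arm, 160 randomised.
- 95% power: 105 evaluable per arm; 105 / 0.8 = 131.25, rounded up to 132 per arm, 264 randomised.

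**Step 6: the misprint reading.** If BWL alone gives about 0.5 point (Section 2.4), the predicted difference is 1.5 − 0.5 = 1.0 point. The 1.5 for the combined arm is also the sum of the two background figures, 0.5 + 1.0. On that reading everything agrees except the printed BWL reduction of 1 point.

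**The case against.** The strongest reply is that the power calculation is sound and one number is misprinted. Section 2.4 supports this, since a BWL reduction of 0.5 restores a 1-point difference and 95% power. This reading is plausible and should be considered first. It is not confirmed: Section 7.1 also attributes its estimates to earlier work at the centre (reference 75), so 1 point in BWL may be intended. Even if it is a misprint, the text needs correcting.

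A second reply is that power for 1 point does not depend on the predicted means, so the two sentences are not in arithmetical conflict. That is true. What fails is the link between them, and with it the claim that the trial is powered for its expected effect. A trial may be powered for another difference, but then the plan must say why.

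A third reply is that 46% depends on what the SD of 1 describes. The sentence attaches it to the reductions, which is the reading used here. If it were the SD of raw scores, the power for 0.5 point would depend on the correlation between baseline and week 12, which the plan does not give:

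| Assumed correlation | Power, change scores | Power, baseline-adjusted |
|---|---|---|
| 0.3 | 35% | 50% |
| 0.5 | 46% | 58% |
| 0.7 | 67% | 74% |
| 0.85 | 93% | 94% |

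None of these reaches 95%. Baseline WBIS adjustment is also not assured, because Section 7.2 adds a covariate only when it differs between arms and is related to the outcome.

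Finally, treatment is delivered in groups, and Section 7.1 mentions an intraclass correlation without giving its value. Clustering would lower all the figures. As an illustration, assume 12 per group (9.6 after attrition) and an ICC of 0.02 to 0.05. The design effect 1 + 8.6 × ICC is then 1.17 to 1.43, and power falls to about 93% to 87% for 1 point and 40% to 34% for 0.5 point. This does not weaken the point, but any restated power should declare its assumption about clustering.

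**Conclusion.** The concern holds. The powered difference is twice the predicted one, and no other section reconciles them. The 95% is correct for 1 point. For the printed prediction of 0.5 point the power is about 46%, taking SD 1 for the reduction, a two-sided 0.05 t-test, 20% attrition and independent participants. The contradiction itself needs none of these assumptions; only the 46% does. The documents do not show which sentence is wrong. It must be fixed because it is the sole power statement for the primary outcome.

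**What to change.** The sponsor should establish which figure was intended and amend Section 7.1, leaving the sample size at 72.

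- **If the BWL prediction was meant to match Section 2.4:** correct it to about 0.5 point. The predicted difference becomes 1 point and the 95% stands.
- **If 1 point in BWL is intended:** remove the statement that the 95% follows from the estimates, give the reason for powering on 1 point, and add text such as: *With 72 randomised and about 29 per arm evaluable, a two-sided t-test at 0.05 with SD 1 for the week-12 reduction, treating participants as independent, has at least 95% power for a difference of 1 point, 80% for about 0.75 point, and about 46% for the predicted difference of 0.5 point.*

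In either case, state whether the SD of 1 refers to change or to raw scores. Also give the ICC value and show how it entered the calculation, or say that clustering was ignored.

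The cost is wording only, with no added participants and no change to design or analysis. Under the second option the stated power for the expected effect becomes less favourable, and a non-significant result would have to be read in that light.

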### 7.2 Analysis Plan

Data quality and integrity will be checked by assessing the data for missing and out-of-range values with basic statistical procedures, including univariate statistics and visual graphical displays (e.g., scatter plots). We will investigate all questions of data quality and integrity prior to performing any statistical modeling. To test the adequacy of randomization, preliminary analyses will include a comparison of all participant demographic and baseline characteristics by randomized treatment groups (t-tests or Wilcoxon rank sum tests for continuous variables and Chi-Square test or Fisher's Exact test for categorical data). If imbalances are observed, the relevant variables will be included as covariates in the final analyses.

All data will be analyzed under the intention-to-treat principle. Analyses will be two-tailed with a significance level of 0.05, and will be conducted using SPSS version 24.0 or SAS version 9.4. Participants who were randomized but did not attend a group meeting will not be included in the analyses, as they will not have received a dose of treatment. We will include as baseline covariates any variables that differ significantly between the treatment groups at baseline and show significant relationships with the outcome. To assess changes in WBIS scores across the 26-week trial, a mixed effects model will be fit with Treatment Group (*BWL+BIAS, BWL*) as a between subjects factor and Time (*Weeks 12 and 26*) as a categorical within-subjects factor. We will use the group x time interactions with the time main effect to estimate and test treatment group differences at each time point. In fitting a mixed effects model with residual maximum likelihood (REML), a variance-covariance structure must be selected. The criteria for selecting the best form of the variance-covariance structure will be based on criteria such as the Akaike's Information Criterion (AIC). The results from the mixed model will be summarized by mean (SE) for each treatment group at each time point. Residual analyses will be conducted to check for outliers and

influential points and violations in the normality assumption. If violations are detected, variance-stabilizing transformations will be considered.

The second aim of assessing changes in other psychosocial and behavioral outcomes, and the secondary aims of assessing changes in weight loss and cardiometabolic risk factors, will be analyzed using the same methods as described above. Changes in all outcomes will be summarized by mean (SE) for each treatment group at each time point.

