### 5.2 Inclusion/Exclusion Criteria

#### Key Inclusion Criteria

Eligible participants will be men and women ages 18-65 years. Participants must have obesity (defined as a BMI  $\geq 30 \text{ kg/m}^2$ ); report a history of experiencing weight bias as assessed by self-report questionnaire and in-person interview; and have elevated levels of WBI as indicated by an average score of 4 (midpoint) or above on the Weight Bias Internalization Scale (WBIS) and by in-person interview. Participants must be seeking weight loss. If currently taking medications, dosages must be stable for at least 3 months. Participants will be eligible to participate if they exhibit mild to moderate severity of depression, anxiety, or binge eating disorder, as determined by the behavioral evaluation and the screening measures (Beck Depression Inventory-II and Questionnaire for Eating and Weight Patterns; see below for details). Elevated WBIS scores are often associated with these variables. Participants taking anti-depressant medication will be eligible if their dose has been stable for a minimum of 3 months.

Eligible female patients will be:

- non-pregnant, evidenced by a negative urine dipstick pregnancy test
- non-lactating
- surgically sterile or postmenopausal, or they will agree to continue to use a method of birth control during the study

Participants must:

- have a PCP who is responsible for providing routine care
- have reliable telephone service with which to participate in conference calls
- understand and be willing to comply with all study-related procedures and agree to participate in the study by giving written informed consent

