### **6.2 Randomization**

Following the screening visit, participants who meet all eligibility criteria and provide informed consent will be randomized to one of the two treatment groups in a 1:1 ratio by a biostatistician. Investigators and participants will not be blinded to participants' assigned

conditions.

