### **6.3 BWL Intervention**

Participants in this group will be provided with 12 weekly BWL sessions, based on the Diabetes Prevention Program (DPP) manual, followed by 2 every-other-week weight loss maintenance sessions and 2 monthly sessions (for a total of 16 visits over 26 weeks). A diet of 1200-1499 calories per day will be prescribed for participants < 250 lb, and 1500-1800 for those  $\geq 250$  lb. Participants will be instructed to eat a balanced deficit diet with approximately 15-20% of kcal from protein, 20-35% from fat (less than 10% from saturated fat), and the remainder from carbohydrates. Session topics during the first 12 weeks will include self-monitoring, stimulus control, slowing eating, social support, cognitive restructuring, portion sizes, and goal-setting. Those during weeks 13-26 will focus on continued self-monitoring and skills required for weight loss maintenance and relapse prevention. BWL sessions will last 60 minutes, with an additional 30 minutes devoted to discussing recipes and food preparation.

Physical activity will be prescribed at a level consistent with data showing that  $\geq 250$  min/wk is associated with improved long-term weight loss. Activity will begin at week 2 with 60 min/wk, and will gradually progress by 10 minutes over 1-2 week intervals until achieving 150 min/wk by week 12, and 200-250 min/wk by week 26. Participants will be instructed to spread the 150-250 minute doses of activity equally across at least 5 days, and to accumulate their structured physical activity in bouts that are  $\geq 10$  minutes in duration. Moderate intensity will be prescribed with an emphasis on walking; the vast majority of our research participants self-select this form of activity.

Participants who cannot attend any given group session will be offered a brief (10-20 minute) make-up session during the week with the group leader or a study staff member. Participants may also meet briefly with the group leader individually, outside of group sessions, up to 3 times during the initial 12-week study period if they have not lost at least 1% of their body weight by week 4, report difficulty controlling their eating, or describe other challenges preventing them from adhering to the program that cannot be fully covered during group sessions.

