## 6.6 Outcome Measures

**Primary outcome.** *Weight bias internalization.* Participants will complete the WBIS (described previously) at screening and weeks 12 and 26 (as well as at week 52). Secondary weight bias and stigma questionnaires will include the Fat Phobia Scale (a measure of stereotype endorsement) and the Weight Self-Stigma Questionnaire (WSSQ), which is another measure of weight bias internalization. The WBIS, Fat Phobia Scale, and WSSQ are widely used and well validated. Additionally, an assessment of weight stigma coping strategies will be completed to assess the frequency with which participants engage in adaptive and maladaptive behaviors (e.g., exercising more vs. avoiding physical activity) in response to weight stigma. At baseline, participants will also complete the Everyday Discrimination Scale, which is a 10-item assessment of unfair treatment in daily life for a variety of reasons including weight, and the Weight Stigma Timing of Life Questionnaire developed for this study assessing experiences of weight stigma at different developmental stages.

**Secondary outcomes.** Participants will complete the Impact of Weight on Quality of Life Questionnaire-Lite (IWQOL), which contains five subscales that include items assessing distress due to weight-stigmatizing situations and weight-based discrimination. Participants will also complete the Perceived Stress Scale (PSS) to determine self-reported daily stress, the Eating Disorders Examination Questionnaire (EDE-Q) to assess disordered eating, the Patient Health Questionnaire (PHQ-9) to assess symptoms of depression, and the Generalized Anxiety Disorder-7 questionnaire to assess symptoms of anxiety. Participants will also complete the Appearance Subscale of the Multidimensional Body-Self Relations Questionnaire (MBSRQ-AS) and the Body Appreciation Scale as measures of body image, and the Rosenberg Self-Esteem Scale. Rejection sensitivity will also be measured at baseline, and treatment acceptability will be assessed at week 26. Participants in the BWL + BIAS intervention group are predicted to show greater reductions in all measures of stigma and distress than participants in the BWL group at weeks 12 and 26 (and at week 52).

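### The plan claims intention-to-treat but drops randomized participants who attend no group meeting, and it plans no outcome analysis of everyone randomized

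*Combined protocol and SAP*

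**What the plan says.** Section 7.2 (Analysis Plan) sets the principle: "All data will be analyzed under the intention-to-treat principle". Two sentences later it restricts the set: "Participants who were randomized but did not attend a group meeting will not be included in the analyses". The reason given is that such people received no treatment. The primary model is a mixed model for WBIS with "Time (*Weeks 12 and 26*) as a categorical within-subjects factor". The closing paragraph of 7.2 says that the other psychosocial and behavioral outcomes, weight and cardiometabolic outcomes "will be analyzed using the same methods as described above".

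Four other places bear on the point:

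- Section 6.2 (Randomization): "Investigators and participants will not be blinded" to assignment.
- Section 6.3 (BWL Intervention): "Participants who cannot attend any given group session will be offered a brief (10-20 minute) make-up session". Section 6.4 extends this to the BWL + BIAS arm.
- Section 5.2 (Key Inclusion Criteria): participants must "have elevated levels of WBI as indicated by an average score of 4 (midpoint) or above" on the WBIS. Section 6.6 confirms that the WBIS is completed at screening.
- Section 6.5 (Outcome Assessment Visits): questionnaires can be completed online or returned by mail.

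**The concern.** Intention-to-treat keeps each randomized person in the assigned arm, whatever treatment that person takes up. Excluding people for something they did after randomization breaks this, and a prespecified reason does not restore it. The plan names one analysis set and defines another.

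The exclusion causes selection bias only if never-attendance differs by arm, in number or in kind, and is related to outcome. In an unblinded trial that cannot be ruled out. The arms differ in a 30-minute segment, stigma content against recipes, and section 6.7 lists distress from discussing stigma as a risk. If never-attendance is alike in both arms, the rule only removes dilution from non-adherence. The plan asks for neither never-attender counts and characteristics by arm nor an all-randomized analysis, so it has no planned way to tell the two cases apart.

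**Working it through.** **1. The text, side by side.** The principle covers all data. The exclusion covers all analyses, and the closing paragraph of 7.2 carries it to the other outcomes. The one comparison of the groups as randomized in 7.2 concerns demographic and baseline characteristics, not outcomes. No section plans an outcome analysis of all 72.

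**2. The stated reason.** Someone seen only in make-up sessions has attended no group meeting, so the wording excludes that person even though treatment was received.

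**3. Why deleting the sentence is not enough.** The Time factor has only weeks 12 and 26. A never-attender with no follow-up WBIS adds no outcome row to the model, with or without the exclusion. No missing-data assumption is stated.

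**4. The plan's own power figure.** Inputs from section 7.1: 36 per arm, 20% attrition, SD 1, difference 1 point, two-sided alpha 0.05. With data: 36 × 0.8 = 28.8 per arm. The standard error of the difference is √(2/28.8) = 0.264. Power is 96.7% by the normal approximation and 96.2% by the t-test, so the stated 95% is reproduced.

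**5. Illustration of dilution.** From section 7.1: mean reductions μ = 1.5 (BWL + BIAS) and 1.0 (BWL), a predicted difference of 0.5. Assumed: k never-attenders of 36 in an arm; never-attenders do not change; a share p = 0.8 of attenders has week-12 data; a share q of never-attenders has week-12 data. The contrast is treated as a difference in mean change.

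Shift in one arm's mean reduction from excluding them = μ × kq / [(36 − k)p + kq]. The change in the group difference is the BWL + BIAS shift minus the BWL shift. With q = 0.8 the shift reduces to μk/36.

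Example, k = 4 in each arm and q = 0.4: 1.6/(25.6 + 1.6) = 0.0588, and (1.5 − 1.0) × 0.0588 = 0.029.

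| Never-attenders, BWL + BIAS / BWL | q = 0.8 | q = 0.4 | q = 0 |
|---|---|---|---|
| 1 / 1 | +0.014 | +0.007 | 0 |
| 2 / 2 | +0.028 | +0.014 | 0 |
| 4 / 4 | +0.056 | +0.029 | 0 |
| 4 / 0 | +0.167 | +0.088 | 0 |
| 0 / 4 | −0.111 | −0.059 | 0 |

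**6. Scale, for q = 0.8.** Equal numbers: 3% to 11% of the predicted 0.5 points, or 1.4% to 5.6% of the 1 point used for power, and 0.05 to 0.21 standard errors. 4 versus 0: 33% or 17%, and 0.63 standard errors. 0 versus 4: −22% or −11%.

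**7. Effect on power of keeping everyone.** Assume a 1-point difference among attenders, equal numbers of never-attenders per arm with no between-arm difference among them, and 28.8 per arm with data. The expected difference is then 1 × (1 − k/36), which is 0.97, 0.94 or 0.89 for k = 1, 2 or 4. T-test power is 95.2%, 94.1% or 91.2%, against 96.2% for k = 0.

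**The case against.** The rule is disclosed, with its reason, in the same paragraph as the principle, so a careful reader can recognize a modified intention-to-treat set. The only certain defect is the label; any effect on the result is conditional. Arm-related non-attendance may also be unlikely. Both arms have the same schedule, 90-minute meetings and 60-minute core, all participants are seeking weight loss, and the documents do not say when people learn their assignment. Because weight is taken at every meeting, attendance by arm should be on file.

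The larger figures need extreme inputs: 4 versus 0, an 80% reply rate among people who never came, and no improvement in any of them. The illustration also places never-attenders on top of 20% attrition among attenders, although the plan's 20% may already include them. With k = 4 per arm, q = 0.4 implies 1 − 27.2/36 = 24% missing, and q = 0 implies 1 − 25.6/36 = 29%.

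Most of this stands as a limit on size. It does not remove the contradiction: disclosing an exclusion does not make the analysis intention-to-treat, and attendance records on file are not a planned analysis of them. It is also fair that a new model specification goes beyond the labelling defect. The core remedy does not depend on it.

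**Conclusion.** The concern holds: as written, the plan does not deliver the intention-to-treat analysis it claims, and it plans no outcome analysis of everyone randomized. Confidence in the contradiction is high. The size of any effect is unknown, because the documents give neither the number of never-attenders nor how they differ.

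Under the stated assumptions the dilution is small with equal numbers per arm, at most 0.056 points, and zero if nobody fails to attend. It is about zero under the model as written if never-attenders supply no follow-up data. The most unbalanced case considered reaches 0.63 of a standard error. These figures describe dilution only; selection bias could go either way and cannot be sized. This should be fixed, because it concerns the primary analysis set and the remedy is cheap.

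**What to change.** **Core changes**

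- Delete the exclusion sentence and define the primary analysis set as all randomized participants in their assigned arm.
- Seek week-12 and week-26 questionnaires from never-attenders online or by mail, routes that section 6.5 already allows.
- State the missing-data assumption for the mixed model (missing at random).
- Report never-attender counts and baseline characteristics by arm.
- Keep the attended-at-least-one-meeting set as a sensitivity analysis labelled modified intention-to-treat, and state whether a make-up session counts as attendance for it.

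**Useful additions**

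- Enter the screening WBIS as a baseline response, so that every randomized participant contributes a row, and say whether baseline means are constrained equal across arms. For people with no follow-up this adds little information about the week-12 contrast.
- Because missing at random treats non-replying never-attenders like others in their arm, add a sensitivity analysis that sets them to no change from screening. Describe it as pessimistic: entry requires a score of 4 or above, so some regression to the mean is expected.

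**Cost.** SAP wording, including a model change if the baseline response is adopted; a few mailings; and one added sensitivity analysis. The estimate may be slightly diluted, by 0 to 0.056 points for up to 4 never-attenders per arm in equal numbers. Non-repliers stay missing, and weight, blood pressure and waist may stay missing for people who never come in.
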